### **7.2 Patient disposition**

Patient disposition information will be summarized by treatment group and overall. The number of patients who were enrolled will be shown in the overall summary, further the number and percentage of patients who received at least one infusion with study drug, who ended the study but continued treatment with study IVIG/SCIG and who terminated treatment with study IVIG/SCIG will be presented. The primary reason for early withdrawal will also be tabulated. The number of patients treated will be used as the denominator for the percentage calculation.

A table of patient disposition will also be generated by study centre and country.

The study duration (in months) of an individual patient will be calculated as (Maximum(Date of close-out visit, date of last infusion with IVIG/SCIG) - Date of first infusion with IVIG/SCIG + 1)/30.4375 and will be summarized by treatment group and overall in the Safety population.

Patient disposition will be listed.

## 7.3 Demographics and baseline characteristics

### 7.3.1 Demographics

Age (years), height (cm), weight (kg) and BMI (kg/m^2) at baseline will be summarized descriptively by treatment group and overall in the Safety population. The baseline weight will be defined as the weight measured before the first IVIG/SCIG infusion. Age category (categorized by age groups < 18, 18-43, 44-68, and > 68 years), race and sex will be summarized by counts and frequencies.

In addition, demographic characteristics will also be presented by diagnosis.

### 7.3.2 Baseline and disease characteristics

The underlying diagnosis and its severity as assessed by the investigator will be summarized by treatment group and overall in the Safety population. For the diagnosis the following pre-specified categories will be considered if at least one patient with this diagnosis is included in the Safety population:

- Primary Immunodeficiency (PID)
- Secondary Immunodeficiency (SID)
- Immune Thrombocytopenic Purpura (ITP)
- Guillain-Barré Syndrome (GBS)
- Chronic Inflammatory Demyelinating Polyradiculoneuropathy (CIDP)
- Multifocal Motor Neuropathy (MMN)
- Myasthenia Gravis (MG)
- Multiple Sclerosis (MS)
- Dermatomyositis (DM)
- Polymyositis (PM)
- Pemphigus Vulgaris (PV)
- Toxic Epidermal Necrolysis (TEN)
- Other.

The presence of pre-specified concomitant diseases/risk factors at baseline will be summarized descriptively by treatment group and overall in the Safety population. The following concomitant diseases/risk factors will be considered:

- History of previous thromboembolic events (yes/no)
- Atherosclerosis (yes/no)
- Coronary artery disease (yes/no)
- Impaired cardiac output (yes/no)
- Obesity (yes/no)
- Diabetes (yes/no)
- Hypertension (yes/no)

- Hyperlipidemia (yes/no)
- Coagulation disorders (yes/no)
- In-dwelling catheters or devices (yes/no)
- Immobilization (yes/no)
- Known or suspected blood hyperviscosity (yes/no)
- Other cardiovascular risk factor(s) (yes/no)
- Other relevant concomitant diseases (yes/no).

Previous thromboembolic events and other relevant concomitant diseases will be coded by MedDRA Version 23.0 or higher and summarized by System Organ Class (SOC) and Preferred Term (PT) in the Safety population. The sort order will be by decreasing frequency in the overall group by SOC and then by PT within SOC. These summaries will also be generated by diagnosis.

For patients with diagnosis PID or SID the history of recent infectious episodes within the last 12 months before study observation start is recorded in the eCRF. In case any recent infectious episodes have been observed, patients are asked regarding the infected area and the number of infectious episodes in this area using the following pre-specified categories:

- Serious infections of the upper respiratory tract
- Serious infections of the lower respiratory tract
- Urinary tract infections
- Bacteremia/sepsis
- Bacterial meningitis
- Osteomyelitis/septic arthritis
- Bacterial pneumonia
- Visceral abscesses
- Other infectious diseases.

The occurrence of any recent infectious episodes, the occurrence of any recent infectious episodes in each of the above categories, the total number of recent infectious episodes and the total number of recent infectious episodes in each of the above categories will be summarized by treatment group and overall in the Safety population. These summaries will be generated for the pool of PID/SID patients and for each of the two diagnoses separately.

As cases of bacterial pneumonia actually are always recorded as cases of serious infections of the lower respiratory tract as well, the former will not be counted in the calculation of the total number of recent infectious episodes.

In case that a certain type of infection has occurred but the pertaining number of infectious episodes is missing this number will be set to one.

All baseline and disease characteristics will be listed.

### 7.3.3 Previous and concomitant medications

Previous and concomitant medications will be coded according to WHO Drug Dictionary, version 19.1 (B3 format). Concomitant medications will be summarized by preferred name and ATC level 2 in the Safety population. For this analysis a medication will be considered as concomitant if it cannot be excluded that it is given after the first IGIV/SCIV infusion in the study up to the close-out visit. That is, only medications with a stop date before the first IGIV infusion or a start date after the close-out visit will be excluded from the summary of concomitant medications. All previous and concomitant medications will be listed.

Details for imputing missing or partial start and/or stop dates of medications for the purpose of determination of the status as previous/concomitant are described in Section 7.2.2.

Previous treatment for the underlying primary diagnosis will be summarized by preferred name and ATC level 2 separately for (i) patients with PID and SID and (ii) patients with any other diagnosis in the Safety population.

For patients with PID/SID the previous treatment with immunoglobulins (within 6 months before study start) will be summarized by drug name, treatment group and overall.

For patients with other diagnoses than PID or SID any previous treatment (within 6 months before study start) will be summarized by drug name and ATC level 2.

These summaries will also be generated by diagnosis.

All previous treatments for the underlying diagnosis - including also non-drug therapies and other blood products - will be listed.

## 7.4 Extent of exposure

### 7.4.1 Treatment duration

Treatment duration (in months) will be calculated as (last infusion date – first infusion date + 1)/30.4375, regardless of study drug interruptions.

Treatment duration will be summarised by treatment group and overall in the Safety population using descriptive statistics. A summary of treatment duration will also be provided by diagnosis.

### 7.4.2 Exposure to study drug

For each patient the following measures will be calculated and summarized with descriptive statistics by treatment group and overall in the Safety population:

- Number of IVIG/SCIG infusions.
- Number of IVIG/SCIG infusion courses. An infusion course is defined as a sequence of infusions that are given over consecutive days with allowed gaps of 3 days without

documented infusions, i.e. a new course starts when there are at least 4 days without documented infusions.

- Complete dose (in g and g/kg body weight).
- Mean dose per infusion (in g and g/kg body weight).
- Mean dose per infusion course (in g and g/kg body weight).
- Average infusion rate (in mL/kg body weight/hr).
- Maximum infusion rate (in mL/kg body weight/hr).

In the eCRF only the volume (in mL) of an infusion is captured. To calculate doses in grams the following transformations will be applied:

For octagam® 5% the dose in grams per infusion will be calculated as infusion volume (mL) x 0.05 as octagam® 5% contains 50 mg protein per mL of solution. For octagam® 10% the dose in grams per infusion will be calculated as infusion volume (mL) x 0.1 as octagam® 10% contains 100 mg protein per mL of solution. Panzyga® comes as a 10% solution ready for intravenous administration; hence the dose in grams per infusion will also be calculated as infusion volume (mL) x 0.1. Cutaquig® is a sterile solution of human normal immunoglobulin containing 16.5% (165 mg/mL) protein, hence the dose in grams per infusion will be calculated as infusion volume (mL) x 0.165. To get the dose per kg body weight the dose in grams will be divided by the body weight (in kg) as determined at the respective infusion visit. In case the weight is missing the following rules will be applied:

- (i) Use the weight measured at the latest preceding infusion visit.
- (ii) If no weight measurements are made at any preceding infusion visit use the weight from the first visit on which weight was measured.

For each patient the complete dose (in g or g/kg body weight) is calculated as sum of the doses (in g or g/kg body weight) over all infusions and the mean dose per infusion (in g or g/kg body weight) as arithmetic mean of the doses (in g or g/kg body weight) over all infusions. The mean dose per infusion course (in g or g/kg body weight) is defined by (i) summing up all doses (in g or g/kg body weight) over an infusion course and then (ii) calculating the arithmetic mean of these summed-up doses over all infusion courses.

The infusion rate (in mL /kg body weight/hr) per single infusion will be calculated as infusion volume (mL)/(duration of infusion (hr) x weight (kg)), missing weights will be imputed as described above. The average infusion rate for a patient will be determined as the arithmetic mean of the infusion rates over all infusions.

For each infusion visit, the maximum infusion rate is recorded in the eCRF. Maximum infusion rates can be reported in four different units: mL/min, mL/hr, mL/kg body weight/min, and mL/kg body weight/hr. The following transformations will be applied to get the maximum infusion rate in mL/

kg body weight/hr:

Original Unit	Transformation
mL/min	x 60 / weight (kg)
mL/hr	/ weight (kg)
mL/kg body weight/min	x 60
mL/kg body weight/hr	No transformation necessary

Missing weights will be imputed as described above. For the tabulation the maximum of the maximum infusion rate over all infusions will be determined for each patient.

All summaries of exposure measures will also be generated by diagnosis.

All infusion details as recorded in the eCRF will be listed.

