Patients are treated with octagam®, panzyga® or cutaqui® according to the Investigator's prescription. For dosage recommendations please refer to the local octagam®, panzyga® or cutaqui® package leaflets.

Dosage and duration of treatment is at the sole discretion of the Investigator and will depend on the type and/or severity of the disease and the patient's clinical condition.

In case of SCIG home treatment the Investigator should promote compliance by instructing the patient to take cutaqui[®] exactly as prescribed and by stating that compliance is necessary for the patient's safety. The patient should be instructed to contact the Investigator if he/she is unable for any reason to administer cutaqui[®] as prescribed.

All dosages of octagam[®], panzyga[®] or cutaqui[®] that a patient received during the observation period at the study center are to be recorded on the corresponding eCRF pages. Dosages of cutaqui[®] that a patient administered during the observation period at home are to be recorded in the patient diary and will be entered into the eCRF later. It is of utter importance that all data entered into the diary are checked by the Investigator for completeness and any safety-relevant issues (including infusion site reactions) during each patient's visit to the study center.

Any drug dose adjustment and interruptions should be recorded on the corresponding eCRF page.

If, for any reason, the Investigator or the patient decide to discontinue the treatment with octagam[®], panzyga[®] or cutaqui[®], the observation period of this patient will be terminated. Efforts should be made to arrange a close-out visit. The reason(s) for termination in the eCRF is to be documented. Switching from one Octapharma Ig product to another Octapharma Ig product is possible without termination of the study but should be documented.

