## **3 STUDY DESIGN**

### **3.1 General study design**

This is a prospective, multicentre, non-interventional study (NIS).

The treating physician decides whether, how and for how long a patient is to be treated with octagam®, panzyga®, and/or cutaquinig®.

octagam®, panzyga®, and/or cutaquinig® will be prescribed regularly to any patient who needs to be treated with an IgG product because of their medical condition and whom the treating physician wants to include in this observational study, after the decision has been made to prescribe IVIG or SCIG treatment. This study will observe 300-500 patients treated with octagam®, panzyga® and/or cutaquinig® in any indication, age group, gender or treatment regimen. It is not possible to specify the exact number of doses per patient that are to be documented because of the different indications for use.

This observational study is conducted in outpatient and inpatient centres globally.

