### **3.3 Study treatments and assessments**

Patients documented in this NIS will receive commercially available octagam®, panzyga® or cutaquinig® prescribed by a physician. Dosage and duration of treatment is at the sole discretion of the investigator and will depend on the type and/or severity of the disease and the patient's clinical condition.

Due to its non-interventional and observational nature, this study will strictly exclude predefined visits or time schedules (except that a close-out visit should take place before a patient leaves the NIS). However, it is recommended to perform subsequent visits on regular intervals according to standard treatment procedures for the respective disease. Table 1 lists all assessments recommended by the protocol.

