## **7 STATISTICAL METHODS**

### **7.1 General statistical conventions**

All statistical procedures will be completed using SAS version 9.4 or higher.

Continuous variables will be summarized using descriptive statistics, including number of subjects (n), mean, median, standard deviation (SD), minimum and maximum.

For categorical variables, summaries will include counts of patients and percentages. Percentages will be rounded to one decimal place.

All summaries will be presented by treatment group and overall, unless otherwise specified. As patients are allowed to change the study drug during the course of the study, treatment groups can be defined that are composed of more than one treatment depending on which patterns of treatment change will actually be observed. In case that such treatment groups are defined, summary tables by visit or summary tables for events that occur within the study will contain more than one column for these composed treatment groups. A patient will be summarized in the column that belongs to the actual treatment that the patient received at the respective visit or at the onset of the respective event.

All patient data, including those derived, will be presented in individual patient data listings. Unless otherwise stated, unscheduled visit results will be included in date/time chronological order, within patient listings only. All listings will be sorted by centre, patient number, date/time and visit (if applicable). The treatment group as well as patient's sex, age and diagnosis will be stated on each listing. Unless otherwise stated, data listings will be based on the Safety population.

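### The infusion-course rule in SAP 7.4.2 breaks down for frequent subcutaneous dosing: if infusion dates are never more than 4 days apart, mean dose per course equals the complete dose

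*SAP*

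**What the plan says.** SAP 7.4.2 lists "Number of IVIG/SCIG infusion courses" among the exposure measures. Up to 3 infusion-free days may fall inside a course, and "a new course starts when there are at least 4 days without documented infusions". The mean dose per course is obtained by adding the doses within each course and then "calculating the arithmetic mean of these summed-up doses over all infusion courses". The complete dose is the sum over all infusions.

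The measures are tabulated by treatment group and overall, and "All summaries of exposure measures will also be generated by diagnosis". Neither SAP 6.1 nor SAP 7.4.2 has a separate rule for subcutaneous infusions, a limit on course length or a break when the product changes.

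The regimen is open. SAP 3.1 admits patients "in any indication, age group, gender or treatment regimen", and SAP 3.3 states: "Dosage and duration of treatment is at the sole discretion of the investigator". Under Protocol 4.1, cutaquig doses given at home "are to be recorded in the patient diary and will be entered into the eCRF later", so each one counts as a documented infusion.

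**The concern.** The rule suits intravenous treatment given in blocks of days separated by weeks. Subcutaneous treatment may be spread evenly, and the rule then gives a result that depends on spacing rather than on dose. If no two successive dates are more than 4 days apart, the course never closes. The mean dose per course then duplicates the complete dose in the same table and measures length of follow-up.

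If such schedules occur, the number of courses and the mean, SD and maximum of dose per course can mislead in the cutaquig, overall and by-diagnosis columns. The pooled columns would mix intravenous treatment episodes with whole-study subcutaneous totals.

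**Working it through.** **Inputs.** The course rule and dose definitions come from SAP 7.4.2. The documents give no subcutaneous interval, dose or group size. The schedules, the 6.6 g per week and the group of 50 below are assumptions for illustration only.

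**The rule as a formula.** Infusion-free days = difference between successive dates − 1. A new course starts when this is at least 4, so dates 4 days apart (3 free days) stay in one course and dates 5 days apart (4 free days) start a new one. Averaging the course sums gives

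mean dose per course = complete dose / number of courses.

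With all differences at most 4 days, the number of courses is 1 and the two measures coincide. As a check, 20,000 random date sequences with differences of 1 to 4 days each gave exactly one course.

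**Course counts over 52 weeks.** The last column removes each infusion in turn and counts how often the number of courses rises.

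| Schedule | Infusions | Courses | Removals that split a course |
|---|---|---|---|
| Daily | 364 | 1 | 0 of 364 |
| Every 2nd day | 182 | 1 | 0 of 182 |
| Every 3rd day | 122 | 1 | 120 of 122 |
| Every 4th day | 91 | 1 | 89 of 91 |
| Mon/Wed/Fri | 156 | 1 | 102 of 156 |
| Mon/Thu | 104 | 1 | 102 of 104 |
| Mon/Wed | 104 | 52 | 0 of 104 |
| Every 5th day | 73 | 73 | not run |
| Weekly | 52 | 52 | 0 of 52 |
| Every 14 days | 26 | 26 | not run |
| IV, 5 days every 28 days | 65 | 13 | not run |

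The intravenous pattern comes out as intended. Mon/Wed and Mon/Thu differ only because Wednesday to Monday is 5 days, whereas Thursday to Monday is 4. On Mon/Wed/Fri the splits come from 51 Mondays and 51 Fridays; losing a Wednesday leaves a 4-day difference and no split.

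**Dose per course at 6.6 g per week.**
- Complete dose: 6.6 × 52 = 343.2 g.
- Weekly or Mon/Wed: 343.2 / 52 = 6.6 g per course.
- Mon/Thu: 343.2 / 1 = 343.2 g per course. At 26 weeks it is 6.6 × 26 = 171.6 g, and at 104 weeks 6.6 × 104 = 686.4 g.
- Ratio at 52 weeks: 343.2 / 6.6 = 52, whatever the dose. For 3.3 to 13.2 g per week the Mon/Thu value runs from 171.6 to 686.4 g.
- Mon/Thu with one infusion undocumented and the course split: (343.2 − 3.3) / 2 = 169.95 g.

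**Effect on a column of 50 patients**, unaffected patients at 6.6 g and affected patients at 343.2 g:
- 1 affected: mean (49 × 6.6 + 343.2) / 50 = 13.3 g, SD 47.6 g.
- 5 affected: mean (45 × 6.6 + 5 × 343.2) / 50 = 40.3 g, SD 102.0 g.
- The median stays at 6.6 g for up to 24 affected. At 25 it is (6.6 + 343.2) / 2 = 174.9 g.

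**Change of product.** Take six 5-day intravenous courses followed by 26 weeks of Mon/Thu subcutaneous infusions. If the first subcutaneous infusion falls 4 days after the last intravenous day, there are 6 courses, the last holding 5 intravenous and 52 subcutaneous infusions. If it falls 5 days after, there are 7 courses.

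**The case against.** The strongest reply is that no affected patient has been shown. Neither document states a subcutaneous interval, and cutaquig may be a small part of the 300–500 patients: Protocol 1.1 calls it newly licensed and names only Canada as approving it. That stands, and it is why the size in this study cannot be given.

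Second, little depends on the rule. The primary endpoint is the incidence of adverse drug reactions, with patients and infusions as denominators (SAP 7.6.1). No tests are planned, and efficacy does not use courses. A reader would also see one course beside 104 infusions in the same table, and all infusions are listed. This keeps the point minor, but it does not correct a misleading mean, SD or maximum in an analysis that is descriptive throughout.

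Third, calling uninterrupted therapy one course is a literal and internally consistent reading. But the same weekly amount then gives values 52-fold apart depending on weekdays. At fixed intervals of 5 days or more, the measure only repeats the mean dose per infusion. It adds nothing useful for regular subcutaneous dosing of either kind.

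Fourth, Protocol 4.1 requires diary checks for completeness and Protocol 7.1 provides for queries, so undocumented infusions should be few. That is fair; the sensitivity to one entry follows from the main problem and is not a separate defect.

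Last, SAP 7.1 provides for switching: "As patients are allowed to change the study drug during the course of the study, treatment groups can be defined" that combine products. If they are, courses spanning two products fall in those groups and in the overall and by-diagnosis columns, not under cutaquig alone. The SAP still does not say how such a course is divided.

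**Conclusion.** The concern holds, as a minor point. For any patient whose infusion dates are never more than 4 days apart, SAP 7.4.2 makes the mean dose per course identical to the complete dose. This follows from the definitions and needs no assumption about dose. The 52-fold ratio assumes 52 weeks of Monday/Thursday rather than Monday/Wednesday or weekly infusions; the gram figures also assume 6.6 g per week.

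How many patients are affected is unknown. Subcutaneous treatment given weekly or less often is unaffected, as are columns with intravenous products only. Number of infusions, complete dose and mean dose per infusion do not depend on the rule, and the median of the course measures may not move.

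**What to change.** In SAP 7.4.2, restrict number of courses and mean dose per course to intravenous infusions, and do not pool subcutaneous infusions into them in the overall or by-diagnosis columns. Apply the restriction to infusions rather than patients, so that a patient who switches contributes only the intravenous part. For cutaquig, rely on the number of infusions, complete dose and mean dose per infusion already planned.

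The cost is one or two sentences and minor programming, with no new data. There would be no course-based figure for cutaquig. The two rows need their own n, because patients treated only with cutaquig drop out of them, and for switchers the course count will not match the total infusion count beside it. Courses that run across two intravenous products would still merge.

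A dose per week on cutaquig, counting subcutaneous periods only, could be added if a rate is wanted. The divisor must be stated. With (last date − first date + 1), the weekly dose is overstated for short series:
- Weekly infusions: 2 × 7 / 8 = 1.75-fold at 2 infusions, 4 × 7 / 22 = 1.27-fold at 4 and 52 × 7 / 358 = 1.02-fold at 52.
- Mon/Wed infusions: 7 / 3 = 2.33-fold at 2, 14 / 10 = 1.40-fold at 4 and 364 / 360 = 1.01-fold at 104.
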